Until very recently LNP syndromes were hardly recognized as being a distinct clinical entity within the broad range of NP syndromes. However, LNP syndromes are much more frequent than often perceived. Up to 83% of patients suffering from PHN complain of an LNP syndrome. Considering all clinical entities of NP, recent epidemiological studies clearly indicate that in approximately 60% of patients it affects a specific, clearly demarcated area of the body and can be described as 'localized neuropathic pain' (LNP). This means that up to 431,151 individuals may be suffering from LNP in Belgium. In order to help physicians distinguish LNP from other types of neuropathic pain, the following definition of LNP was proposed in 2010, based upon the broader IASP definition of NP: 'A type of peripheral neuropathic pain that is characterized by consistent and circumscribed area(s) of maximum pain associated with abnormal sensitivity of the skin and/or spontaneous symptoms characteristic of neuropathic pain, for example, burning pain'. 10 By identifying patients with LNP this definition facilitates an evidence-based approach to the management of NP. Instead of treating these LNP conditions with systemic treatment options, these conditions can be treated more effectively by topical treatment. It should be stressed that topical treatment refers to pharmaceutical agents that act locally on the peripheral nervous system, in contradiction to medications such as buprenorphine and fentanyl that can be applied to the skin, but which exert their effect on the CNS following transdermal systemic absorption. Such topical route offers significant advantages over systemic administration. Notably, only a small fraction of the dose reaches the systemic circulation, thereby reducing the risk of systemic adverse effects, drug-drug interactions and overdose.

In current routine clinical practice, patients with neuropathic pain conditions (including LNP) are still treated with oral pharmacological drugs as first-line therapy, as recommended by national and international guidelines. However, hardly one-third of these patients seem to achieve satisfying and clinically relevant analgesia. When increasing drug dosage also fails to reduce pain, treatment is adapted to a drug from a

¹ International Association for the Study of Pain.

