Currently, the standard approach to all types of neuropathic pain – including the localized neuropathic pain syndromes – is the use of systemic treatment options. However, such systemic treatment often (in a vast majority of patients) leads to systemic side effects such as nausea, vomiting, dizziness, sedation and peripheral edema. These side effects are extremely uncomfortable for the patients and have a high negative impact on their overall quality of life (which is already negatively impacted by the disease state). It is therefore important for patients to avoid the occurrence of systemic side effects. ⁵³ Providing a topical treatment to their localized neuropathic pain syndromes allows patients to avoid systemic side effects, since no systemic absorption occurs during topical administration of analgesic substances. These considerations are especially important since neuropathic pain syndromes are almost always chronic in duration, so long-term (chronic) therapeutic options have to be provided.

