3.5 Secondary endpoints

- Long term quality of life profile;
- Reduction in pain intensity (PI-NRS);
- Time to worsening of the pain and use of rescue medication for pain (MQS III-R);
- Global perceived effect (GPE);
- Effect on mood (Hospital Anxiety and Depression Scale);
- Quality of sleep (NRS and ISI);
- Percentage of patients without systemic drug related side effects (dizziness, fatigue, vertigo, somnolence, headache, blurred vision);
- Time to discontinuation of the study drug and proportion of patients stopping the drug;
- Participation in activities (Utrecht Work Engagement Scale-9);
- Impact of pain on functioning (interference BPI);
- Work Productivity and Activity Impairment (WPAI: Neuropathic Pain, v2.2, Belgium);
- Neuropathic Pain Symptom Inventory (NPSI).

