7.4 Blinding

No blinding is necessary for this open label trial.

Blinded assessment for the 3 treatment arms seems impossible in this case considering the clear difference in treatment modalities for the three therapeutic regimens. There is only one systemic treatment, versus two topical treatment solutions. In addition, the two topical treatment strategies differ significantly from each other (daily application versus three-monthly application, no skin reaction compared to neurogenic inflammation during a couple of hours after application of capsaicin). As such trial participants, pharmacists and care providers are unblinded to intervention groups.

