7.7 Trial assessments

The study comprises a screening period of maximum 21 days, randomisation (d-21 to d-1), a baseline visit at day 0 (start of treatment), a treatment period of 24 weeks and a post-treatment period of 2 weeks (24-26 weeks). Considering the pragmatic nature of the proposed trial clinic visits are kept to an absolute minimum.

The **clinical visits** take place at day 0 (V1), week 4 (V2), 12 (V3), 18 (V4), 24 (V5) and 26 (V6) which is comparable to a schedule which would be maintained in routine clinical care. A deviation of +/- 5 days is allowed for the clinical visits. The assessments made at these visits are (*routine care assessments are indicated in bold):*

- Documentation of the study intervention: number of patches (lidocaine and capsaicin), location, dosage used (pregabalin and gabapentin), compliance and discontinuation check
- Documentation of size of painful area
- Assessment of adverse events
- Assessment of systemic drug related side effects (e.g. dizziness, fatigue, vertigo, somnolence, headache, blurred vision) (not on baseline visit)

- · Concomitant medication use
- Only during V2 and V4 clinical sensory testing will be repeated (using the Boston Bedside Quantitative Sensory Testing Battery)

The majority of the assessments (patient reported outcomes and experiences) will be performed by making use of an online platform, enabling patients to complete the different assessments themselves without having to schedule a clinic visit. The use of the online platform will significantly reduce the work load for the patients involved in this study. Per regular weekly online assessment, the required time investment will not exceed 15 minutes. The online assessments on a monthly basis (n = 7 in total) will never require more than 30 minutes (which can be split over different moments).

Online assessments: weekly basis

A deviation of max. 48 hours is allowed for the completion The following procedures and assessments will be carried out:

- Assessment of reduction in pain intensity using PI-NRS
- Assessment of analgesic medication use (using MQS III)
- Quality of sleep: Sleep NRS
- Assessment of systemic drug related side effects (not collected at baseline)
- Discontinuation of study drug (not collected at baseline)
- Participation in activities: Utrecht Work Engagement Scale-9

Online assessments: monthly basis (baseline, week 6, 10, 14, 18, 22)

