- The percentage of systemic drug-related side effects will be evaluated at 6 and 26 weeks using Chi-square test or Fisher's exact test. The evolution of the percentage of systemic drug-related side effects over time will be analyzed using a generalized linear mixed effects model using the clinical visit data and

the self-reported patient data.

- Discontinuation of study drug or study withdrawal: the percentage of study
 withdrawal will be compared after 6 and 26 weeks with a Chi-square test or
 Fisher's exact test whatever is appropriate based on assumptions. The time to
 discontinuation will also be studied in a time-to event analysis comparing the
 different treatment arms. The self-reported patient data will be used for this.
- Global perceived effect (GPE), effect on mood (Hospital Anxiety and Depression Scale), quality of sleep (Sleep-NRS and ISI), participation in activities (Utrecht Work Engagement Scale-9), impact of pain on functioning (interference – BPI), and Work Productivity and Activity Impairment (WPAI-Neuropathic Pain) will be compared at 26 weeks using linear regression and over time using linear mixed models.
- Similar to the primary outcome the treatment effect on the secondary outcomes will be estimated in a model with adjustment for confounders and including site as a random effect

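### The tolerance endpoint counts 'drug related' systemic side effects without saying whether, by whom or how relatedness is judged, which in this open-label trial lets attribution differ by arm in favour of the patches

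*Protocol*

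**What the plan says.** Section 3.5 of the protocol lists the secondary endpoint as "Percentage of patients without systemic drug related side effects (dizziness, fatigue, vertigo, somnolence, headache, blurred vision"), a closed list of six symptoms. Section 7.7 has the visit item "Assessment of systemic drug related side effects (e.g. dizziness, fatigue, vertigo, somnolence, headache, blurred vision) (not on baseline visit"), the same six symptoms but as examples. A weekly online self-report item has the same name and also no baseline value. Section 7.8 confirms that neither is collected at baseline. In section 7.7 the visit item stands apart from the general adverse event assessment.

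Section 10.3.3 sets the test: "The percentage of systemic drug-related side effects will be evaluated at 6 and 26 weeks using Chi-square test or Fisher's exact test". It models the course over time with a "generalized linear mixed effects model using the clinical visit data and" the patients' self-reports. Section 7.4 says that "trial participants, pharmacists and care providers are unblinded to intervention groups".

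On absorption, section 2 argues that topical treatment avoids systemic side effects "since no systemic absorption occurs during topical administration of analgesic substances". Section 1 says that "only a small fraction of the dose reaches the systemic circulation".

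**The concern.** Comparing tolerance between systemic and topical treatment is a stated secondary objective (section 3.2), and avoiding systemic side effects is the central argument of section 2. If relatedness is part of the outcome, its value depends on what the reporter believes about the treatment as well as on whether the symptom occurred.

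Dizziness, fatigue, somnolence and headache are common and non-specific. Section 6 allows analgesics and antidepressants in every arm, so background symptoms are to be expected. A reporter who knows the arm, and who thinks a patch cannot act systemically, has little reason to call such a symptom drug related under a patch and every reason to do so under pregabalin. The recorded difference would then partly reflect the belief under test. Analysis cannot recover symptoms that were never reported because the question asked only for drug-related ones.

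**Working it through.** **What the text fixes and what it leaves open.**

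| Question | Protocol |
|---|---|
| Is the endpoint labelled drug related? | Yes: summary, 3.5, 7.7, 7.8, 10.3.3 |
| Is a relatedness judgement described for it? | No |
| Who would judge, and by what rule? | Not stated |
| Do reporters know the arm? | Yes (7.4) |
| Baseline value? | No (7.7, 7.8) |
| Symptom list | Closed in 3.5, examples in 7.7 |
| Systemic absorption from patches | None (2); a small fraction (1) |

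**Who reports at each test.** Clinic visits fall at day 0 and weeks 4, 12, 18, 24 and 26. None falls at week 6, so a point assessment there rests on patient self-report. At week 26 and in the longitudinal model, both sources are available.

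**The plan's own figure, used only as an input.** With effect 0.08, SD 0.240, alpha 0.05/2 and 80% power, the normal approximation gives 2 × (2.2414 + 0.8416)² × (0.240/0.08)² = 171.1, so 172. The t-test gives 172.35, so 173 as stated. With 12% dropout, 173/0.88 = 196.6, so 197 per arm, and 3 × 197 = 591. The stated sample size reproduces and is not in question.

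**Illustration of differential attribution.** The protocol gives no symptom rates or attribution shares for this endpoint, so these are assumptions:

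- b: true symptom rate, the same in both arms
- full attribution under pregabalin, so p1 = b
- r: share attributed under a patch, so p2 = b × r
- n = 197 per arm, two-sided 5%, pooled two-proportion z test (equivalent to the Chi-square test)

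With p̄ = (p1 + p2)/2, the chance of significance in favour of the patch is approximately

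Φ{ [(p1 − p2)√n − 1.96 √(2 p̄(1 − p̄))] / √(p1(1 − p1) + p2(1 − p2)) }.

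For b = 20%, with √197 = 14.036:

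- r = 0.5 (20% v 10%): (1.404 − 1.96 × 0.505)/0.500 = 0.83, Φ = 0.80
- r = 0.75 (20% v 15%): (0.702 − 1.96 × 0.537)/0.536 = −0.66, Φ = 0.26
- r = 0.9 (20% v 18%): (0.281 − 1.96 × 0.555)/0.555 = −1.45, Φ = 0.073; the opposite tail adds 0.007, giving 0.08

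Summing the exact binomial probabilities gives the same rounded values, and neighbouring assumptions give:

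| True rate b | r = 1 | r = 0.9 | r = 0.75 | r = 0.5 |
|---|---|---|---|---|
| 10% | 5% | 6% | 14% | 48% |
| 20% | 5% | 8% | 26% | 80% |
| 40% | 5% | 13% | 55% | 99% |

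Two variations for b = 20%. With alpha 0.025, the r = 0.5 case falls to about 71%. With incomplete attribution in both arms (80% v 60%, so 16% v 12%) and 173 per arm, the chance is about 19%. Equal attribution returns the nominal 5%.

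**The case against.** The strongest reply is that no attribution step appears in the text. Section 11.3.1 says the platform records the occurrence and intensity of symptoms and mentions no causality field. Section 9.1 makes causality an explicit data item only for SAEs and SUSARs. The items may therefore be a plain symptom checklist on which drug related is only a label. The questionnaire itself is not shown.

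The absorption sentence in section 2 is also rationale, not an instruction to raters. Where the protocol does govern causality, section 9.2 points to medical judgement and the Reference Safety Information. Appendix 2 treats an event as a reaction whenever a causal link cannot be ruled out. Both apply to every arm.

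Much of this stands. A reader might infer that the endpoint counts only events judged drug related, that investigators must follow section 2, or that a symptom counts under pregabalin and never under a patch. The documents support none of these. Nor do they support certain false significance. Even with no patch attribution at all and a 5% symptom rate, Fisher's exact test (one of the plan's two tests) is significant in about 93% of trials at 197 per arm, and mild differences in attribution add little.

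The gap remains. The causality rules in section 9.2 and Appendix 2 are not tied to this endpoint. Neither is the trial-independent physician's causality review for the steering committee, which is also not described as blinded. If the items are a plain checklist, the endpoint's name is wrong. If they are not, the rule is missing. Leaving detail to a SAP does not settle it, because the wording of the question determines what is collected.

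**Conclusion.** The concern holds as a badly fixed endpoint that carries a real risk of bias towards the patches. It is not a demonstrated bias, and the protocol does not contain a rule that treats the arms differently. At week 6 the bias would arise through patient self-report. At week 26 and in the longitudinal model, clinic staff can contribute too.

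Its size cannot be derived from the protocol. On the central assumptions above, the chance of a spurious significant difference is about 8%, 26% or 80% for patch attribution of 90%, 75% or 50%, so it ranges from slight to dominant. The sample size and the primary endpoint are unaffected. The change is worth making because tolerance is a stated objective and the remedy is cheap.

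**What to change.** - In sections 3.5, 7.7 and 10.3.3, define and test the endpoint as the occurrence of any symptom on one closed list since the last assessment, whatever its attributed cause. Use identical wording in all arms and in both the online and the visit items.
- Add the same item to the existing baseline questionnaire so that pre-existing symptoms can be accounted for.
- Report events attributed to the drug descriptively only, and state who attributes them and by what rule.
- Reconcile sections 1 and 2 on systemic absorption from the patches.

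The cost is revised endpoint wording, relabelled items and one additional baseline item. Background symptoms will raise the rate in all arms and slightly dilute the contrast. Unblinded reporting of the symptoms themselves remains, so open-label bias is reduced but not removed.

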Planned Trial Period		21 months between first patient first visit and last patient last visit, 27 months till Clinical Study Report.				
	Objectives	Endpoints				
Primary	To determine if topical treatment significantly improves health-related quality of life compared to systemic treatment in adult patients suffering from localized neuropathic pain across a wide variety of etiologies (LNP), with a duration between 1 and 24 months.	Change in EQ-5D-5L from baseline to 6 weeks.				
Secondary	To compare the effectiveness in terms of pain relief between the treatment arms. To compare the	Reduction in pain intensity (PI-NRS), time to worsening of the pain (PI-NRS and NPSI) and use of rescue medication (MSQ III-R). AUC for EQ-5D-5L				
	effectiveness in different aspects of quality of life between the treatment arms.	measurements, global perceived effect (GPE), effect on mood (HADS), quality of sleep (NRS and ISI).				

To compare the drug Percentage of patients tolerance between without systemic drug related side effects. systemic and topical treatment. percentage of patients who discontinue the study drug. To identify the difference Impact of pain on between topical and functioning (Interference – systemic treatment in terms BPI), participation in of functional status of the activities (Utrecht Work Engagement Scale-9). patient. Work Productivity and Activity Impairment (WPAI). Interventions Topical treatment 1: lidocaine 5% medicated plaster (Versatis) Topical treatment 2: capsaicin 8% patch (Qutenza) Systemic treatment: pregabalin (generics) **Description of the** Topical treatment 1: daily administration of lidocaine 5% intervention or medicated plaster, during 12 consecutive hours, with a Formulation. Dose. maximum of 3 plasters at the same time. **Route of Administration** Topical treatment 2: capsaicin 8% patch, periodic of IMP administration upon reoccurrence of pain symptoms (mostly after 90 days), in a hospital setting during maximum 1 hour. Maximum number of patches is equal to the number needed to cover the painfull area. The surface of this area cannot be larger than 520cm2. Systemic treatment: pregabalin (oral administration), dose determined by up-titration in first 4 weeks with a maximum daily dose of 600mg.

FUNDING AND SUPPORT IN KIND

KCE is the only funder of this study. No commercial funding for this study.

ROLE OF STUDY SPONSOR AND FUNDER

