Vomiting	1 – 2 episodes (separated by 5 minutes) in 24 hours.	3 – 5 episodes (separated by 5 minutes) in 24 hours.	>=6 episodes (separated by 5 minutes) in 24 hours; tube feeding, TPN or hospitalization indicated.	Life- threatening consequences; urgent intervention indicated.	Death
Dizziness	Mild unsteadiness or sensation of movement.	Moderate unsteadiness or sensation of movement; limiting instrumental ADL.	Severe unsteadiness or sensation of movement; limiting self care ADL.	-	-
Depressed level of consciousness	Decreased level of alertness.	Sedation; slow response to stimuli; limiting instrumental ADL.	Difficult to arouse.	Life- threatening consequences.	Death.

If cross-over of active treatment (pregabalin to gabapentin, lidocaine to capsaicin or capsaicin to lidocaine) occurs as well as if active treatment is stopped, the corresponding visits will be performed as described in the flow chart. The patient remains in the study and will be followed up as if he/she was still on active treatment.

All withdrawals will be documented and the reason for withdrawal recorded in the patient file (medical record) and in the eCRF and discussed, as necessary, in the clinical trial report.

Patients who fail screening will not be included in the analysis but will be entered into the

trial database (eCRF – OpenClinica). The reason for failure will be documented in the patient file and in the eCRF and reported descriptively and by patient listing in the report of this trial.

Patients who fail screening will be replaced. Patients who initially may not meet eligibility criteria (e.g. for administrative reasons or assessments are out of time window) may be re-screened at investigator's discretion after consulting with the Sponsor (CI). Patients who withdraw from the study after randomisation will not be replaced.

The sponsor reserves the right to discontinue the trial overall or at a particular trial site at any time for the following reasons:

- Emergence of any efficacy/safety information that could significantly affect continuation of the trial;
- Violation of good clinical practice (GCP), the clinical trial protocol (CTP), or the contract by a trial site or investigator, disturbing the appropriate conduct of the trial.

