7.12 End of trial

A patient is considered to have completed the trial in case any of the following applies:

- Completion of planned follow-up period
- Lost to follow-up, after 3 attempts to reach the patient. The attempts should be documented in patient record.
- Refusal to be followed-up (e.g. if patients discontinues the study due to adverse events but refuses to be followed up)
- Withdrawal of informed consent

The end of the entire trial will occur when one of the following situations occurs:

- When all patients have completed their follow-up period or are lost to follow-up.
- If the trial is ended by the sponsor for any reason when patients are still being treated with a clinical benefit, the patients will be offered treatment in a follow-up trial which will allow patients to continue to receive treatment as long as the treating investigator deems it appropriate.
- If the trial is terminated by the sponsor for safety reasons.

The main Ethics Committee will be notified of the end of trial by the sponsor within 90 days.

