10.3.2 Primary outcome analysis

The primary outcome EQ-5D-5L at 6 weeks will be compared between the 3 treatment arms in first instance using a linear regression model with treatment as a predictor and correction for quality of life at baseline. All patients in the study will be used in an intention-to-treat (ITT) analysis.

Patients who withdraw from the study medication are offered a different treatment option of topical or systemic treatment respectively. Following standard care practice patients on the pregabalin arm will be offered an alternative systemic drug (gabapentin) and patients on the topical arm will be offered a different topical drug (failing treatment with lidocaine 5% medicated plasters will be treated with capsaicin patches and otherwise) Cross-over between topical and systemic treatment is not allowed to maximally preserve the treatment

effect between the two methods. Non-compliers and withdrawals are followed up according to the protocol. Their data will be collected in the same way as for the adherers and in the analysis they will be considered in the initially randomised treatment arm.

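### Section 10.3.3 compares the percentage of study withdrawal, although the endpoint is the proportion of patients stopping the study drug

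*Protocol*

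**What the plan says.** **Endpoint.** The protocol's trial summary puts "percentage of patients who discontinue the study drug" under the drug-tolerance objective. Section 3.5 lists "Time to discontinuation of the study drug and proportion of patients stopping the drug". Both parts of the endpoint concern the drug.

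**Analysis.** The item in section 10.3.3 opens with "Discontinuation of study drug or study withdrawal: the percentage of study" and continues "withdrawal will be compared after 6 and 26 weeks with a Chi-square test or" Fisher's exact test. It then adds that the time to "discontinuation will also be studied in a time-to event analysis comparing the" arms, and ends by naming patient self-report as the data source.

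**What happens after stopping.** Section 7.11 says of a patient whose active treatment is switched or stopped: "The patient remains in the study and will be followed up as if he/she was still on active treatment". Section 10.3.2 agrees: "Non-compliers and withdrawals are followed up according to the protocol".

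**Expected rates.** Section 10.1 gives follow-up completion of 90% and 96% from two earlier studies. Separately, it gives rates of withdrawal from study medication by drug, and expects these to be considerable in the systemic arm because of side effects.

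**The concern.** The percentage test names a different event from the endpoint it is meant to serve. Someone who stops pregabalin for side effects but goes on completing questionnaires, as the protocol asks, has met the endpoint but has not withdrawn from the study. If the programmer follows section 10.3.3 literally, that patient is a non-event. The result would describe retention in the trial, while a reader of section 3.5 would take it for drug stopping.

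This is not a detail left for a later analysis plan, because the protocol names a variable and it is not the endpoint variable. The trial is open label, so the choice between two possible codings should be fixed before anyone sees the data by arm.

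**Working it through.** **1. The definitions side by side.**

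| Place in protocol | Event |
|---|---|
| Trial summary; section 3.5 | Stopping the study drug |
| Section 10.3.3, item heading | Stopping the drug, or study withdrawal |
| Section 10.3.3, percentage at weeks 6 and 26 | Study withdrawal |
| Section 10.3.3, time-to-event analysis | Discontinuation |

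Sections 7.11 and 10.3.2 keep drug stoppers in follow-up, so the first and third rows count different patients.

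**2. The plan's own figures.** Section 10.1 gives no power for this endpoint, so the sample size was checked first. With a difference of 0.08, SD 0.240, two-sided alpha 0.025 and 80% power, the exact two-sample t-test needs 172.4, rounded up to 173 per arm. Then 173/0.88 = 196.6, rounded up to 197, and 3 × 197 = 591. All three stated figures reproduce. The pooled pregabalin rate also reproduces: (39 + 41)/(153 + 277) = 80/430 = 18.6%. The others are 9/155 = 5.8% (lidocaine) and 6/282 = 2.1% (capsaicin).

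**3. Power if drug stopping is tested.** Expected stops at 197 per arm are 197 × 0.186 = 37, 197 × 0.058 = 11 and 197 × 0.021 = 4. The formula, with p̄ the mean of the two proportions, is

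power = Φ{ [|p1 − p2| − z·√(2p̄(1 − p̄)/n)] / √([p1(1 − p1) + p2(1 − p2)]/n) }.

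- Pregabalin v lidocaine at alpha 0.05: (0.128 − 1.96 × 0.03298)/0.03234 = 1.96, so power is 97.5%.
- Pregabalin v capsaicin at alpha 0.05: (0.165 − 1.96 × 0.03069)/0.02955 = 3.55, so power is above 99.9%.

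| Drug stopping, 197 per arm | alpha 0.05 | alpha 0.025 |
|---|---|---|
| 18.6% v 5.8% | 97.5% | 95.3% |
| 18.6% v 2.1% | >99.9% | 99.9% |
| 14.8% v 5.8% (lower single-study pregabalin rate) | 83.9% | 76.0% |
| 14.8% v 2.1% | 99.6% | 99.1% |
| 5.8% v 2.1% (lidocaine v capsaicin) | 47% | 36% |

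**4. Power if study withdrawal is tested.** Completion of 90% and 96% implies 4% to 10% overall loss. These are rates from two studies, not two arms, and the protocol gives no arm-specific rate. The splits below are therefore assumptions, used only for illustration at alpha 0.05:

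- equal arms: rejection at about the 5% level only;
- 7% v 5%: 13%;
- 10% v 8%: 10%;
- 10% v 4%, the extreme of the range: 65%.

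**5. The time-to-event analysis in the same item.** Assume proportional hazards and take the hazard ratio from the cumulative proportions. Against lidocaine, HR = ln(1 − 0.186)/ln(1 − 0.058) = 3.44, with 197 × (0.186 + 0.058) = 48 events. Power = Φ(√(48.07/4) × ln 3.44 − 1.96) = Φ(2.33) = 99%, or 98% at alpha 0.025. Against capsaicin, HR is 9.7 with 41 events, and power is above 99.9%.

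**The case against.** The strongest reply is that this is loose wording. The item's heading names drug discontinuation. Its closing sentence points to patient self-report, and the matching weekly item in section 7.7 is discontinuation of the study drug. The protocol also uses withdrawal for stopping medication elsewhere, in sections 7.11 and 10.1. A slip is therefore plausible. Usage is not uniform, however, since section 7.11 also speaks of patients who withdraw from the study after randomisation. The literal text remains open to two codings, so the need for a correction stands.

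The second reply limits the consequence, and it is right. A reader might infer that the plan misses the expected difference altogether, or that the tolerance objective is answered only by a retention figure. The documents do not support that. The time-to-event analysis covers the first half of the section 3.5 endpoint and is well powered. Section 10.3.3 also tests the percentage with systemic drug-related side effects at weeks 6 and 26 and models it over time.

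Two further inferences fail. One is that the design deliberately keeps retention equal across arms. Section 10.1 expects only high completion because the follow-up burden is low, and says nothing about equality. The other comes from section 7.12, which says "A patient is considered to have completed the trial in case any of the following applies" and then includes loss to follow-up, refusal and withdrawn consent. The label is awkward, but section 7.12 does not define study withdrawal and no analysis in section 10.3 refers to it. That is a clerical matter and no part of this point.

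**Conclusion.** The point holds for the percentage comparison alone. As written, that test does not measure the proportion stopping the study drug and is not aimed at the expected differences of 12.8 points (18.6 − 5.8) and 16.5 points (18.6 − 2.1). Aimed at drug stopping, it would have power of 97.5% and above 99.9% at alpha 0.05. Severity is minor to moderate: the defect affects one half of one secondary endpoint, and leaves the primary analysis, the sample size and data collection untouched.

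The drug-stopping rates come from earlier studies whose follow-up may not match weeks 6 and 26. The power loss from testing study withdrawal cannot be stated as a single figure, because any arm split is an assumption.

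**What to change.** In section 10.3.3, make the percentage compared at weeks 6 and 26 that of patients who discontinued their allocated study drug. State whether a switch to another drug counts as discontinuation. State also that the scheduled end of treatment at week 24 is not itself an event in the week-26 figure. Use the same event definition for the time-to-event analysis. Report study withdrawal separately, by arm and reason, in the CONSORT diagram that section 10.3.1 already plans.

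The cost is a few words in one item. Drug discontinuation is already asked weekly (section 7.7), and withdrawals with their reasons already go into the eCRF (section 7.11), so no new data are needed.
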